Exclusion criteria:

- Unable to comprehend the consent form fully, respond adequately to screening questions, or maintain focus or to sit still during assessment.
- Primary psychotic disorder, and disorders requiring more specialized care such as: severe eating disorders, substance use disorders, uncontrolled medical conditions, marked cognitive impairment, or severe neurological disorder.
 - Note: Substance use is expected in this adult population. Exclusion will be only for substance abuse or dependence that is so severe that it interferes or would foreseeably interfere with the ability to complete assessments or intervention.
- Previous participation in STAND research studies

Preliminary eligibility is established during the account creation process. If responses to the self-report questions in screening indicate the individuals may have a substance use disorder, psychosis, or active suicidality, they will be contacted by staff to further assess eligibility for this program, and resources/referrals for care may be provided if they are determined ineligible for this study. If they are found eligible after assessment, they will be provided a link to re-enter the screening process to complete surveys, then receive a randomized condition assignment and information about proceeding to their recommended level of care. Further confirmation of insurance coverage may be required in the case that a participant is assigned to receive clinical care. If they do not have eligible insurance coverage, they are informed of ineligibility at that time. Participants who are treated by a mental health professional (such as a psychiatrist, psychologist, therapist, etc.) during time that treatment is offered through STAND and unwilling to fully transfer care to STAND, will not be eligible to receive clinical services, but may continue participating in the study through receiving surveys. If there are changes to their current treatment status they may be offered to transition care to STAND, or they may be transitioned to other levels of care (tiers 1 or 2) as recommended by their condition assignment (SSD or DDD). Eligibility may be reassessed throughout the study by research staff, coaches or care providers. If at any time a participant is found to not meet eligibility criteria, they will be informed of ineligibility and removed from study.

Study Overview

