Study participation is completely remote and lasts 40 weeks after initial orientation/intake. Participation requires creating an online account on the STAND at ELAC study website in order

to complete eligibility screening. Once initial eligibility is confirmed, those who choose to participate must sign an online consent form and complete baseline assessments. Upon completion of baseline assessments, participants are randomized to 1 of 2 treatment conditions (SSD or DDD), and assigned to a level of care based on their responses to baseline surveys. Participants must attend a remote orientation or intake session for their assigned level of care, and thereafter are asked to complete weekly online surveys over the course of 40 weeks. Participants are considered enrolled after completing consent, baseline assessments, and attending an orientation/intake session for their assigned level of care.

Condition Assignment

Participants in this study will be randomized into one of two conditions which are differentiated by approach for decision making in treatment triage and treatment adaptation. The standard approach used in previous STAND studies is **symptom severity-based decision making (SSD)**. SSD participants will be triaged and adapted to level of care based on reported symptom severity only.

The experimental approach is **data-driven decision making (DDD)**. DDD participants will be triaged and adapted to a level of care using a multivariate predictive algorithm that is iteratively updated annually. This algorithm determines level of care based on individual participant characteristics, coupled with reported symptom severity. The DDD *triaging* algorithm will be implemented beginning in Year 1 of this project and the DDD *adaptation* algorithm will be implemented beginning in Year 2.

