For receiving care, participants will be assigned to one of the three services: Wellness (Tier I), Digital Mental Health and Coaching (Tier II) or Clinical Care (Tier III) based on the criteria of their randomized condition - SSD or DDD. Participants in both conditions will be asked to complete short surveys online weekly, and longer online survey assessments every 8 weeks. At every assessment time point participants are asked to complete the CAT-MH (computer adaptive tests) which provides validated symptom scores for depression, anxiety, mania/hypomania, substance use, psychosis, and suicidality. See **Table 1** for a description of CAT-MH depression and anxiety scores and their clinical interpretation. The information about depression and anxiety symptoms collected during these CAT-MH assessments will be used to inform adaptation of care in accordance with the criteria of participant's randomized condition, SSD or DDD.

Participants assigned to tiers 2 & 3 (in both SSD and DDD conditions) will additionally be randomized to receive usual risk management (URM) or usual risk management with the addition of a technology-enhanced suicide prevention intervention (TE-SPI).

Table 1 CAT-MH Symptom Scores

	Depression (CAT-DI)	Anxiety (CAT-ANX)
Normal	0 - < 35	0 - < 35
Mild	35 - 65	35 - 50
Moderate	> 65 - 75	> 50 - 65
Severe	> 75 - 100	> 65 - 100

In **SSD, triaging** will be determined solely by scores on CAT-DI (depression symptom severity), CAT-ANX (anxiety symptom severity) and CAT-SS (suicide risk severity). CAT-DI and CAT-ANX

provide cutoffs for none, mild, moderate and severe categories. From CAT-SS (suicidality), participants who endorse suicidal ideation with either intention or plan are considered at risk, and are offered Tier III clinical care. Otherwise, Tier assignments in SSD are made based on the following criteria:

- Tier I self-guided prevention (Wellness): Participants with less than mild depression or anxiety and without suicidality.
- Tier II (Digital Mental Health with Coaching): Participants with mild to moderate depression or mild to severe anxiety, without suicidality.
- Tier III (Clinical care): Participants with severe depression or endorsement of suicidality.

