Active recruitment will take place during each academic year at ELAC. Promotional activities as outlined above will continue during the rest of the academic year as necessary for maintaining awareness about the study on the college campus. Materials related to these strategies and specific to this research study are uploaded to the online IRB application. Note that in these materials, we have explicitly limited the times we discuss the affiliation of the study with UCLA. Many community college students seek admission to UCLA and might become concerned about disclosing mental health information prior to learning about the confidentiality limits discussed in the informed consent form, and thus not engage with the present research study.

Prospective participants who have provided their contact information will be contacted (via email, phone call or text message) by study staff within 14 business days to review study eligibility and research procedures. Participants in this stage may be guided by staff or automated prompts to continue their enrollment process as needed.

Study enrollment has a target sample of approximately 200 participants per year. Additionally, for this study, we require the following allocation per service across both conditions per year: n = 20 for Wellness, n = 120 for Digital Mental Health + Coaching, n= 60 for Clinical Care. Once the desired sample size per service is reached for the research study, upon review, enrollment may conclude for the academic year and students will be referred out for alternative services if needed. Care may continue to be available through the STAND for All (non-research) program. Participants may be placed on a wait list for the research study in the case that a spot in their recommended care service is expected to become open within a clinically acceptable timeframe.

Consent

Participants sign research consent prior to their assignment to the recommended level of care. This study utilizes the REDCap eConsent framework to collect electronic signatures from

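### Service quotas and wait-listing act on a tier known only after SSD/DDD randomisation, so a full service can remove or delay randomised students differently by arm

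*Protocol*

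**What the plan says.** **Order of steps.** Study Overview: "Upon completion of baseline assessments, participants are randomized to 1 of 2 treatment conditions (SSD or DDD), and assigned to a level of care". The text after the exclusion criteria gives the same order for students cleared by staff, who "then receive a randomized condition assignment and information about proceeding to their recommended level of care".

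**Tier depends on arm.** Under Condition Assignment, the service is set "based on the criteria of their randomized condition - SSD or DDD". SSD triage "will be determined solely by scores on CAT-DI (depression symptom severity), CAT-ANX (anxiety symptom severity) and CAT-SS (suicide risk severity"). DDD triage uses the symptom scores together with four further clusters of variables.

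**Point of enrolment.** Study Overview: "Participants are considered enrolled after completing consent, baseline assessments, and attending an orientation/intake session for their assigned level of care".

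**Quotas.** Study Procedures, Recruitment: "we require the following allocation per service across both conditions per year", followed by 20, 120 and 60. On closing: "Once the desired sample size per service is reached for the research study, upon review, enrollment may conclude for the academic year", with students referred elsewhere if needed. On waiting: "Participants may be placed on a wait list for the research study in the case that a spot in their recommended care service"; the condition there is that such a place should come free soon enough.

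**Analysis.** Specific Aim 1 makes intent-to-treat the primary analysis, and Aim 3 follows the same scheme.

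**The concern.** The count that triggers closing, and the place that decides wait-listing, both refer to a tier that the randomised arm produced. Two students with identical baseline data can be recommended different tiers because they were randomised to different rules. If one of those tiers is full, one student proceeds and the other is delayed or referred out. That is selection on a consequence of the intervention, after randomisation.

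A student stopped this way has been randomised but is not enrolled under the protocol's definition. Elsewhere the protocol lets participants who cannot receive clinical services stay on surveys. It has no matching provision for students referred out for lack of capacity. Without surveys there is no outcome, and an analysis plan cannot recover one later. At stake is the comparability of the arms in Aims 1 and 3.

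**Working it through.** **1. The plan's own figures.** 20 + 120 + 60 = 200 per year, and 200 × 5 = 1,000. Both match the stated targets. The quotas correspond to tier shares of 10%, 60% and 30%.

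**2. Where the gate sits.** The sequence is: consent, baseline, SSD/DDD randomisation, tier under that arm's rule, orientation or intake, enrolled. Quota and wait-list refer to the tier, so they can act only after randomisation. The protocol describes no capacity check before randomisation and no quota by arm.

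**3. How far the retained arms could differ.** The documents do not give the agreement between the DDD and SSD tiers or the times at which services fill. What follows is therefore an illustration on assumptions:

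- Baseline severity S is standard normal, and SSD tiers on S alone.
- DDD tiers on a score with correlation r to S.
- A fraction f of randomised students arrives after one service is full, and those recommended that service are lost.
- There is no true effect of arm or tier.

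With Tier III share p and φ the normal density at the Tier III cut-off, the mean severity of retained students is

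- SSD: -f·φ(p_SSD)/(1 - f·p_SSD)
- DDD: -r·f·φ(p_DDD)/(1 - f·p_DDD)

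*Equal shares, Tier III full.* With p = 0.30, φ = 0.348, and DDD minus SSD = (1 - r)·f·0.348/(1 - 0.30f). For f = 0.4 and r = 0.5: 0.5 × 0.139/0.88 = +0.08 SD.

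| f | r = 1 | r = 0.8 | r = 0.5 | r = 0.3 |
|---|---|---|---|---|
| 0.2 | 0 | +0.01 | +0.04 | +0.05 |
| 0.4 | 0 | +0.03 | +0.08 | +0.11 |
| 0.6 | 0 | +0.05 | +0.13 | +0.18 |

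At f = 0.4 each arm loses the same 0.4 × 0.30 = 12%, yet the arms differ, because different kinds of student are removed. A simulation of 400,000 students per scenario agrees with the table to within 0.005 SD. If the week-8 outcome is 0.6·S plus noise (also assumed), the spurious outcome difference over r = 0.3 to 0.8 is about 0.01 to 0.11 SD.

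*Unequal shares, Tier III full.* Assume DDD recommends Tier III to 45% and SSD to 25%, a mean of 35%.

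- The 60 places fill after 60/0.35 = 171.4 students are randomised. By then 111.4 of the other 140 places are taken.
- Filling the rest takes (140 - 111.4)/0.65 = 44.0 more, so f = 44.0/215.4 = 0.204.
- Turned away: 0.204 × 0.45 = 9.2% of DDD and 0.204 × 0.25 = 5.1% of SSD.
- Retained mean severity: SSD -0.204 × 0.318/0.949 = -0.068; DDD -r × 0.204 × 0.396/0.908 = -0.089r.
- Difference = 0.068 - 0.089r: -0.02 at r = 1, zero near r = 0.77, +0.02 at r = 0.5, +0.04 at r = 0.3.

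*Tier II full instead, equal shares.* The simulated baseline difference is -0.005 to -0.11 SD over the same f and r = 0.3 to 0.8, so the sign reverses.

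*Same rule in both arms with equal shares (r = 1), or the gate before randomisation.* The difference is zero apart from simulation noise of about 0.005 SD.

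**The case against.** The strongest reply is that the closing rule is discretionary and speaks of enrolment concluding for the academic year. If that means all enrolment stops together, both arms stop together and closure creates no difference. This stands as a possible reading. The text does not say it, however, and the wait-list sentence is explicitly about one service.

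Next, nothing shows that the quotas bind. The revision history records removal of the overall cap of 200 per year in June 2024, which fits reading the numbers as targets. This lowers the likely impact, but the current text still calls the per-service allocation required and still links closing to it.

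Third, there are partial safeguards. The primary analysis is intent-to-treat, wait-listing delays rather than removes, and suicidality leads to an offer of clinical care in either arm. The last narrows the difference among the highest-risk students. Who belongs to the intent-to-treat set may properly be left to an analysis plan that is not shown, but whether students referred out for capacity are still surveyed is a matter of conduct.

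A reader might infer that the arm sending more students to Tier III loses more of its severe students and so looks better. The documents do not support that. SSD's Tier III is defined by severe depression or suicidality, whereas DDD mixes in other variables. DDD can therefore lose more students and still retain the more severe group, as the unequal-shares case shows for r below about 0.77. A reader might also set the bias against the 0.26 SD in the power statement. That figure is the end point of a linearly increasing Aim 3 difference, so it is a poor yardstick for a constant offset.

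**Conclusion.** The point holds as a weakness in the order of steps. As written, the protocol allows randomised students to be delayed or referred out because of a tier that their arm produced, and it does not say that they are followed up.

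It does not hold as a demonstrated bias of known sign or size. Under the stated assumptions the retained baseline severity difference (DDD minus SSD) lies between about -0.02 and +0.18 SD with Tier III full. It reverses with Tier II full, and closure produces none if all enrolment stops together. These ranges rest on assumed tier shares, correlations and fill times, none of which the documents give. The amendment is inexpensive and worth making, but the documents do not show that the trial's comparison has already been compromised.

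**What to change.** Amend the Recruitment section in two places.

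1. Apply any capacity stop or wait-list before SSD/DDD randomisation and identically to every student, for example by pausing randomisation for everyone when a service is full. This concerns entry to the randomised comparison only and need not alter access to care outside the study. Quotas on baseline severity strata would not be enough alone: they do not track DDD demand for each tier, so a randomised DDD student could still be recommended a full service.
2. State that any student already randomised who is wait-listed or referred out for capacity continues to receive the scheduled surveys and is analysed in the intent-to-treat set in the randomised arm.

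**Cost.** A short amendment and a change to one step in the enrolment workflow. Enrolment will be slower at times, and realised tier counts may depart from 20/120/60. This protocol version is dated January 2026 and already describes enrolment in Years 4-5, so the first change protects only students still to be randomised. The second also covers students already randomised, where data can still be collected.

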- The Fotonovela Uptake condition introduces participants to a fotonovela, an online booklet that portrays a dramatic story using animated characters and captions. Participants randomized to this condition will be provided the fotonovela in addition to the text and email reminders already used to remind participants to re-engage in the enrollment process. The content of the fotonovela provides psychoeducation about mental health treatment and ways to overcome barriers to service use. The fotonovela will take approximately 10 minutes to view.
- STAND Engagement Navigator Uptake condition includes a brief telephone contact (approximately 10-15 minutes) with an engagement navigator from the STAND program, in addition to the text and email reminders already used to remind participants to re-engage in the enrollment process. The engagement navigator will follow a guide to address potential barriers to service uptake. The engagement navigator will provide an education to: 1) clarify goals of mental health treatment and perceived need, 2) improve self-efficacy, 3) address negative mental health attitudes, and 4) problem-solve barriers to STAND.
- STAND as usual: Participants randomized to the condition “STAND as USUAL” will not receive additional engagement interventions. These participants will continue to receive the text and email reminders to complete baseline assessments and schedule orientation/intake if they have stopped the enrollment process midway.

URM+TE-SPI

Following assignment to signature project tier, eligible participants (those assigned to tiers 2 and 3) will be additionally randomized to either URM or URM+TE-SPI. Those assigned to URM will proceed according to the usual protocol. Those assigned to URM+TE-SPI will be asked to schedule a time to meet with staff via zoom or phone, when staff will introduce the participant to the TE-SPI intervention components. Participants will be contacted to schedule this introduction at least 1x/week for up to 4 weeks before participants are considered non-responsive. Contact may occur via phone call, text, and/or email.

TE-SPI components will be added to existing usual risk management procedures for those randomized to URM+TE-SPI. The TE-SPI components include 1) BRITE app 2) coping plan 3) caring contacts messaging:

- 1) Participants will be asked to download the BRITE app which includes access a customized coping plan (see component 2 below) mindfulness exercises, a mood log, and selected social support contacts. Staff will provide instruction on logging in and navigating the app.
- 2) Coping plans will be individually tailored by staff to each participant during the BRITE app registration process. The coping plan is programmed into the app for participants to use at will. This coping plan includes strategies for regulating painful, distressing, or dysregulating emotions that can lead to unsafe behaviors, urges, or thoughts, intense distress, emotional dysregulation and/or other problems.

3) “Caring Contacts” messages will be sent to participants at least monthly throughout the study. These include text and email messages that communicate care with the goal of enhancing feelings of connectedness/reminding participants that the study team cares and is interested in their well-being.

[figure not shown]
BRITE App & Coping Plan: Staff will work with participants to initially set up their BRITE app account. This includes staff following prompts and working with the participant to build participants’ personal coping plans (10-20 minutes). Individual coping plans are stored in the participant’s BRITE account. The participant will then be guided to download the BRITE app to their phone and their personal coping plan will be accessible in the app. This plan will be developed to focus on coping with intense distress, depression/mood, anxiety, and/or unsafe (suicidal/self-harm) thoughts or urges as appropriate given the participant’s presentation which will be stored in the participant’s BRITE+ app. For participants who present with some SI risk, the coping plan will focus on coping around SI risk/triggers. For those without reported SI risk, the coping plan will focus on their identified treatment target (i.e. anxiety, mood). Participants can further customize the app by uploading support materials (videos, websites, photos) which are saved to the participants phone and not on the app server. Students can set up their own reminders in the app to receive prompts to use the app and can also access the app at any time. After rating their distress level (1-5, 5=most upset), the app offers the student skills and strategies based on these ratings and their coping/safety plan. For participants at the highest distress levels, the app presents the coping/safety plan, including interpersonal support (i.e., contact options for a nominated person of support).

The BRITE app has been approved by the UCLA TRO Risk Assessment team. All data collected by the app will be stored in a secure research environment, UCLA AWS server. The only data that will be stored in the AWS campus cloud server will be the mood thermometer daily log ins and any text that is entered into the app. Participants will be allowed to upload pictures to the app; however, these pictures are not stored on the cloud and are stored locally on their phone. Data on app use (i.e., time spent on app) will be collected through the app and used to describe intervention uptake/use which will be important for evaluating the intervention feasibility and outcome data. We will also collect data on implementation of the coping planning and caring contacts intervention components (e.g. responses received).

Caring Contacts Messages: Additionally, participants randomized to URM+TE-SPI, will also receive caring contact messages via text. Participants will be informed that messages will not be monitored on a 24/7 basis. Staff will communicate that these messages are intended for support only and are not a substitute for therapy or comprehensive interventions. If participants respond to caring contacts messaging requesting additional support or resources, staff may direct participants to their personal coping plans or the usual risk and case management procedures will be followed, and staff may provide referrals to community resources.

Figure 2 URM & URM+TE-SPI

Figure 3. Overview of Project 3 Design for RCT (Years 3 - 5) Comparing Technology-Enhanced Suicide Prevention (TE-SPI) to Usual Risk Management (URM).

Abbreviations. URM, Usual Risk Management; TE-SPI, Technology-Enhanced Suicide Prevention; SSD, Symptom-Severity Decision Making; DDD, Data-Driven Decision Making.

Participants who were randomized to URM+TE-SPI will receive 1 additional survey (BRITE Satisfaction & Usability Survey) at weeks 12 and 40, asking them to rate the perceived helpfulness of the intervention components (BRITE app, coping plan, caring contacts). Data on app use and responses to caring contacts will also be stored.

Assessments

Once participants complete enrollment, they are directed to a unique link to complete baseline assessments. Participants are instructed to complete the baseline assessments before they can be assigned to a service, and may receive reminders from staff to complete their baseline assessments. Participants may be asked to re-do baseline surveys if > 4 weeks has passed between baseline completion and initiation of care in their assigned service tier.

Participants will be asked to complete a brief symptom survey (CAT-MH) as part of their baseline assessment and weekly thereafter. Additionally, they will be asked about current stress (1 item), current financial, housing and food insecurity, and perceived social support.

Online surveys will be administered on a predetermined schedule at baseline, week 8, week 16, week 32 and week 40 post baseline, and will be sent to the participant by email or text message. An additional battery of online assessments will be administered immediately upon treatment termination. Please see **Table 2** for a detailed schedule of assessments. **Table 3** provides a description for each assessment administered in this protocol. Participants may be additionally contacted by staff for qualitative data collection through interviews over the phone or via zoom. Participants who are interested in providing feedback about study procedures may be compensated an additional \$40 for up to 1 hour of interview and discussion.

Although previous work suggests that there is a low likelihood that any of our assessments will result in significant emotional distress, several steps will be taken to provide additional protection against risk. Both at the outset and following completion of the major assessments, participants will be asked if they are experiencing marked distress. In the event that participants endorse significant distress due to the assessments, they will be given the option to be contacted by the study team. Individuals who are very distressed and indicate that they would like contact will be

told that a member of the project team will contact them to make sure they are okay. A member of the project team will contact the participant, ascertain their current condition, determine the need for escalation to the project investigators, or the need for clinical intervention, and arrange appropriate mental health referral (if the patient is not eligible for or interested in participating in the trial), if necessary.

All assessments will be administered online and data will be collected remotely. The STAND technical infrastructure has been developed by the UCLA Depression Grand Challenge. It has undergone security review by both UCLA Information Services and Solutions (ISS) and Los Angeles County Department of Mental Health (LADMH) and has been approved for providing services and collecting assessment data.

Table 2: Schedule of Assessments

Form Name	Baseline*	Orientation	W 1	W 2	W 3	W 4	W 5	W 6	W 7	W 8	Continued frequency
Demographics	X										
HMS Citizenship	X										
Country & City of birth	X										
Ethnic Identity/Racial Identity	X										
Family Pride	X										
Major Experiences of Discrimination	X										
HMS Beliefs About Mental Health	X										
HMS Therapy Seeking Preferences And Satisfaction	X										
Preference Scale	X										
HMS Physical Health Survey	X										
DERS 16	X										
HMS Insurance	X										
Sensory Experiences Screener	X										
PQ-B Psychosis	o										
SUD Screener	X										
LCSWA Assessment SA	o										
Treatment Utilization Form											
Recent Treatment History									X	weeks 16, 20, 24, 28, 32, 36, 40	
HMS Employment	X								X	weeks 16, 24, 32, 40	
WSAS	X								X	weeks 16, 24, 32, 40	
Impact and GPA	X								X	weeks 16, 24, 32, 40	

Family Cultural Conflict	X						X	weeks 16, 24, 32, 40
HMS Needs Assessment	X							week 40
MOS Support	X							weekly
Everyday Discrimination Scale	X		X	X	X	X	X	weekly
Early and Recent Adversity Questionnaire	X						X	weeks 16, 24, 32, 40
Perceived Need	X		X	X	X	X	X	weekly
Willingness to Pay for Mental Health Treatment, Insurance Status	X							
Weekly Stress (Life Stress)	X		X	X	X	X	X	weekly
PHQ Screen	X							
PHQ Short	o		o	o	o	o	o	o-biweekly
GAD Screen	X							
GAD Short	o		o	o	o	o	o	o-biweekly
SADD Screen	X							
SADD Short	o		o	o	o	o	o	o-biweekly
Sleep Screen	X							
Sleep Short	o		o	o	o	o	X	o-biweekly
Agora Screen	X							
Agora Short	o		o	o	o	o	o	o-biweekly
PCL Screen	X							
PCL Short	o		o	o	o	o	o	o-biweekly
PDSS Screen	X							
PDSS Short	o		o	o	o	o	o	o-biweekly
BRITE Satisfaction & Usability ⁺								weeks 12 ⁺ , 40 ⁺
Suicide and Self-Harm Measures	X						X	weeks 16, 24, 32, 40

Credibility/Expectancy Questionnaire	X							
DSM-5 Self Rated Cross cutting symptom measure	X							
WHODAS 2.0	X							
Social Needs Utilization Questionnaire		X	weeks 16, 24, 32, 40					
Modified Cox Treatment Satisfaction Questionnaire			X	weeks 16, 24, 32, 40				
Test My Brain (post registration)	X				X	weeks 16, 24, 32, 40		
CERQ9	X						X	weekly
SAGE Self Report Diagnostic Screen (post registration)	X							
CAT-MH	X	X	X	X	X	X	X	X

* Baseline occurs after consent. The remaining assessment time points are relative to the date of baseline completion of CAT-MH (e.g., 8 weeks after baseline).

o = only administered if indicated as a treatment target for individual participant. Treatment target defined by: baseline "screen" scores for this measure are above defined thresholds
+ only administered to those randomized to receive TE-SPI

Table 3 Description of Assessments

Form Name	Description
Demographics	Healthy Minds Survey (HMS) - 4 Items assessing self-reported Age, Sex at Birth, Gender Identity, Race/Ethnicity
HMS Citizenship	HMS - 2 items questionnaire assessing self-reported citizenship/Immigrant Status and Acculturation
Country & City of birth	HMS - 1 item questionnaire assessing self-reported country & City of Birth
Ethnic Identity/Racial Identity	Multigroup Ethnic Identity Measure - 6 item questionnaire about relationship to ethnic identity
Family Pride	Family Pride (Familismo) - 7 item questionnaire about familial relationships
Major Experiences of Discrimination	12 Item self-report about lifetime experiences with discrimination
HMS Beliefs About Mental Health	10 item questionnaire assessing personal beliefs about mental health treatment
HMS Therapy Seeking Preferences And Satisfaction	7 item questionnaire assessing mental health treatment history
Preference Scale	1 item questionnaire assessing preferred service from presented options for mental health treatment and resources
HMS Physical Health Survey	2 item self-report scale assessing perceived quality of health and diagnosis of select medical diseases/conditions
DERS 16	16 item self-report scale assessing Difficulties in Emotion Regulation (DERS)
HMS Insurance	1 item self-report assessment of Insurance coverage
Sensory Experiences Screener	4 item self-report questionnaire about sensory experiences, used to screen for psychosis
PQ-B Psychosis	40 item self-report questionnaire asking about experiences of psychotic symptoms in the past month
SUD Screener	4 item self-report questionnaire about experiences with substance use in the past month, used to screen for substance use disorders
LCSW Assessment SA	11 item self-report questionnaire about experiences with substance use in the past month
Treatment Utilization Form	Custom, 4 item questionnaire asking if participants received any mental health care external to this study
Recent Treatment History	Custom, 2 item questionnaire asking if participants are receiving mental health care external to this study
HMS Employment	HMS - 1 Item questionnaire assessing employment

WSAS	5 item questionnaire assessing symptom impact on work, school, and relationships
Impact and GPA	HMS - 2 item questionnaire assessing symptom impact on school
Family Cultural Conflict	5 item self-report scale about perceived conflict in family relationships
HMS Needs Assessment	USDA Housing/Food Security questionnaire and Financial Stress questionnaire - 7 item questionnaire assessing food and housing security, financial and personal wellbeing,
MOS Support	4 item self-report questionnaire about perceived availability of social support
Everyday Discrimination Scale	11 item self-report scale assessing frequency of experiences with discrimination
Early and Recent Adversity Questionnaire	Trauma History Questionnaire
Perceived Need	Healthy Minds Survey (1 item), HMS Needs Assessment
Willingness to Pay for Mental Health Treatment, Insurance Status	1 item self-report question about the amount one is willing and able to pay for mental health treatment in a year
Weekly Stress (Life Stress)	1 Item self-report assessment of current stress level
PHQ Screen	Patient Health Questionnaire-2: 3 item self-report survey screening for depressive symptoms
PHQ Short	Patient Health Questionnaire-14:14 item self-report survey assessing depressive symptoms
GAD Screen	Generalized Anxiety Disorder-2: 2 item self-screener for generalized anxiety, customized for this project
GAD Short	Generalized Anxiety Disorder-7, 7 item self-report assessment of generalized anxiety symptoms
SADD Screen	Social Anxiety Disorder Dimensional scale Screener -3 item self-report screening for social anxiety disorder
SADD Short	Social Anxiety Disorder Dimensional scale-10 item self-report assessment of symptoms of social anxiety disorder
Sleep Screen	Custom, 1 item self-report assessing sleep
Sleep Short	PROMIS 7 item self-report sleep disturbance questionnaire
Agora Screen	DIAMOND Agoraphobia Screener, 1 item
Agora Short	Fear Questionnaire (Agoraphobia subscale), 5 item self-report assessment for experiences of agoraphobia
PCL Screen	PTSD Check List- 5 item self-report screening for PTSD
PCL Short	PTSD Check List, Short: 20 item self-report assessing symptoms of PTSD
PDSS Screen	Panic disorder severity scale self-report, brief - 2 item self-report screening for panic disorder
PDSS Short	Panic disorder severity scale self-report - 7 item self-report assessment for symptoms of panic disorder
BRITE Satisfaction and Usability	23 item self-report about experience using the BRITE app and receiving caring contacts messages

Suicide and Self-Harm Measures	Columbia Suicide Severity Scale (11-31 items), adaptive questionnaire assessing suicidal ideation
Credibility/Expectancy Questionnaire	4 item questionnaire assessing treatment expectations
DSM-5 Self Rated Cross cutting symptom measure	23 item scale used to screen for major DSM-5 diagnoses through self-reported symptom experiences
WHODAS 2.0	World Health Organization Disability Assessment schedule – 11 item self-report assessment instrument for health and disability
Social Needs Utilization Questionnaire	17 item questionnaire about personal utilization of social support services available to participants in this program
Modified Cox Treatment Satisfaction Questionnaire	5 item questionnaire about satisfaction with treatment received
CERQ9	Self report 9 items about responses to negative or unpleasant responses
Test My Brain	self-administered online tasks assessing neurocognitive function including: TMB Digit Symbol Matching, TMB Vocabulary, TMB Matrix Reasoning, TMB Choice Reaction Time, TMB Gradual Onset Continuous Performance Test, TMB Multiple Object Tracking, TMB Multiracial Emotion Identification
SAGE Self-Report Diagnostic Screen	Comprehensive, self-report behavioral health diagnostic tool measuring: Depressive Disorders, Manic + Hypomanic, GAD, Panic Disorder, Agoraphobia, Social Anxiety, PTSD, Alcohol use, Cannabis use
CAT-MH	computer adaptive tests which provide validated symptom scores for depression, anxiety, mania/hypomania, substance use, psychosis, and suicidality

Management of Suicidality

Participants complete suicidality assessment as part of the CAT-MH survey in their weekly assessments. In the event that a participant endorses suicidality in any of these assessments, we will implement a multi-level response, starting with an automated alert system built into the online symptom assessment. Upon survey completion, the participant endorsing suicidal ideation will receive an automatic notification that they will be contacted shortly by the study team. Alerts triggered by responses on the assessments indicating an endorsement of significant suicidal ideation will be automatically sent to ProtoCall Services, a 24/7 triage and crisis intervention service provided through contract. ProtoCall Services will initiate outreach with the participant to assess suicidality and provide urgent intervention if needed. ProtoCall services is contracted to provide 3 follow-up contact attempts within 48 hours of alert (6 contact attempts over 72 hours during weekends and holidays.)

[figure not shown]
An automated alert is also sent to the study team. Participants will receive a follow-up call from a member of our clinical team within one business day (Monday-Friday, 8am-5pm) if needed based on information provided by ProtoCall Services (e.g., in case of no contact, or need for further assessment and support). Response to these alerts might be escalated (e.g., calling emergency contact or wellness check). Members of the clinical team performing this follow up may coordinate further care with a clinician if judged an appropriate course of action. All actionable alerts will be

fully documented, along with follow-up and outcome reporting. The consent form will advise participants that staff will monitor responses to the screener and any alerts generated by responses to symptom assessments.

In the event that Protocall Services counselors are unable to reach the participant through their three attempts within 48 hours, UCLA staff will make three additional outreach attempts within the next 48 hours. If both Protocall Services and UCLA staff are unable to reach the participant, the available data will be reviewed by a licensed clinician and they will make a determination about whether to contact the LA County Department of Mental Health Psychiatric Mobile Response Team (PMRT) for a safety check. In such cases where a participant's safety cannot be verified by Protocall Services or UCLA, the ELAC Student Health Coordinator and the ELAC Behavioral Intervention Team (BIT) will be notified. The suicide monitoring workflow is shown below in **Figure 2**.

Figure 3 Suicide Response

Protocol for ProtoCall+UCLA+ELAC+Clinician coordinated response to suicidality alerts triggered by ELAC students while taking the CAT-MH online screening

*UCLA Suicidality coordinator responsibilities marked with blue, ProtoCall responsibilities in yellow, ELAC responsibilities in Red, Clinician responsibilities in green
**All steps will be appropriately documented by ProtoCall and the UCLA Suicidality coordinator (steps with documentation indicated with a purple heart)

